10.3 Pharmacokinetic Parameters

10.3.1 Plasma Pharmacokinetic Parameters

For Group 1 to 4, a total of 13 blood samples will be drawn from each subject for quantitation of ELX-02 for pharmacokinetic analyses: 0.250, 0.500, 0.750, 1.00, 2.00, 4.00, 6.00, 12.0, 24.0, 36.0, 48.0, 72.0, and 168 hours post-dose.

Plasma ELX-02 concentrations data will be used to calculate the following parameters by standard non-compartmental methods:

 AUC_{0-24} : Area under the concentration-time curve from time zero to 24 hours post-dose.

Whenever concentration data is missing for the 24-hour post-dose sample for a

subject, calculation of the AUC₀₋₂₄ must not be done.

 AUC_{0-72} : Area under the concentration-time curve from time zero to 72 hours post-dose.

Whenever concentration data is missing for the 72-hour post-dose sample for a

subject, calculation of the AUC₀₋₇₂ must not be done.

AUC_{0-t}: Area under the concentration-time curve from time zero to the last non-zero

concentration, calculated using the linear trapezoidal method.

AUC_{0-inf}: Area under the concentration-time curve from time zero to infinity

(extrapolated), calculated as $AUC_{0-t}+C_t/K_{el}$, where: C_t = the last observed

non-zero concentration.

Eloxx Pharmaceuticals

C_{max}: Maximum observed concentration.

Residual area Residual area, calculated as 100*(1- AUC_{0-t} / AUC_{0-inf}).

 T_{max} : Time of observed C_{max} .

 $T_{\frac{1}{2} \text{ el}}$: Elimination half-life, calculated as $\log(2)/K_{\text{el}}$ using the natural logarithm.

K_{el}: Elimination rate constant. This parameter will be the negative of the

estimated slope of the linear regression of the log-transformed concentration (natural logarithm) versus time profile in the terminal elimination phase. At least 3 concentration points will be used in estimating K_{el} . The time point where log-linear K_{el} calculation begins $(K_{el\ Lower})$, and the actual sampling time of the last quantifiable concentration used to estimate the K_{el} $(K_{el\ Upper})$ will be reported with the correlation coefficient from the linear regression to

calculate Kel.

CL/F: Apparent total body clearance, calculated as Dose/AUC_{0-inf}.

V_d/F: Apparent volume of distribution, calculated as Dose/(K_{el} x AUC_{0-inf}).

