The Phase 1a studies assessed the impact of ELX-02 dosing on clusterin and KIM-1, biomarkers of early proximal renal tubular injury. Although nephrotoxicity is a known complication of aminoglycoside use, there was no evidence in the completed single-dose studies that injection of ELX-02 affects renal function.

ELX-02 demonstrated linear dose PK in plasma with a short plasma half-life and parameters characteristic of an aminoglycoside. After single SC administrations, ELX-02 was rapidly absorbed with a median  $T_{max}$  of 0.5 hours for the lowest dose of 0.3 mg/kg and of 1 hour for the other doses. The elimination was rapid with mean terminal half-life ( $T_{1/2}$ ) ranging between 2 to 4 hours for lower doses (0.3 to 5.0 mg/kg) whereas mean  $T_{1/2}$  was longer for the highest dose (about 8 hours for 7.5 mg/kg) as expected with the use of a non-compartmental model in a situation of multiple exponential elimination. The decline of plasma concentrations was monophasic at lowest doses whereas it was biphasic for doses of 2.5 and 5.0 mg/kg and multiphasic for dose of 7.5 mg/kg with concentrations longer quantifiable at higher doses. Mean residence time was about 3 to 4 hours and mean apparent body clearance about 6 L/h for all doses. Mean apparent volume of distribution was dose-dependent with values of about

16.9-70.5 L for doses of 0.3 to 7.5 mg/kg. These data suggest a larger distribution with higher doses, not only restricted to extracellular fluids. The inter-subject variability on main plasma PK parameters ( $C_{max}$ ,  $AUC_{0-inf}$ , partial AUCs) was low with CV% ranging from 6.54 to 18.6% for  $C_{max}$  and 7.64 to 18.2% for AUCs.

Renal excretion accounted for a large part of the eliminated drug. Mean percent of ELX-02 recovered in urine over the 48 hours post-dose of collection was 85.2% for IV treatment and ranged from 81.1 to 99.2% for SC doses. For all SC doses, more than 78% of the administered drug was excreted within the 12 hours post-dosing. Mean renal clearance was about 4.8 L/h for IV treatment and ranged between 4.6 to 6.1 L/h for SC treatments.

Further clinical data on ELX-02 from single dose studies are available in the IB.

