### 5.2.2.2 Anticipated Exposure

ELX-02 is primarily eliminated via the kidney similar to what has been observed for other aminoglycosides. The main processes are glomerular filtration and subsequent reabsorption in the kidney. Aminoglycosides are reabsorbed in the proximal tubules in the kidney via megalin, a transmembrane endocytic receptor expressed in epithelial membrane in the kidney as well as other tissues. In addition to megalin, other transporters expressed in the kidney (OCT2 and SGLT2) play a role in the reabsorption of aminoglycosides in the kidney.

A dose of 1 mg/kg of ELX-02 has been selected for the present study as it has been shown to allow for a good characterization of ELX-02 PK profile. In the Phase 1 SAD study noted above, following a single 1 mg/kg SC dose, the mean (N=6)  $C_{max}$  was 3576 ( $\pm$  502) ng/mL, the median  $T_{max}$  was 1.0 (range 1.0-1.0) hours, and the mean  $AUC_{0-12}$  was 13,131 ( $\pm$  1729) ng\*h/mL. The half-life was 2.14 ( $\pm$  2.14) hours, and clearance (CL/F) was 5.50 ( $\pm$  0.349) L/h.

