## **9.9 Sample Collection for Pharmacokinetic Evaluation**

### **9.9.1 Blood Sample Collection and Processing**

A total of 13 blood samples will be drawn from each subject of Groups 1 to 4 for PK analyses. Blood samples will be collected 0.25, 0.5, 0.75, 1, 2, 4, 6, 12, 24, 36, 48, 72, and 168 (Day 8) hours post-dose (up to 6 mL for each sampling time).

The time tolerance window for blood samples will be  $\pm 1$  minute for timepoints up to 2 hours post-dose;  $\pm 5$  minutes from 4 hours to 12 hours;  $\pm 10$  minutes from 24 hours to 72 hours; and  $\pm 24$  hours for the 168-hour sample. Sample collections done outside the pre-defined time windows will not be considered as protocol deviations since actual post-dose sampling times will be used for PK and statistical analyses. Unless otherwise specified or for subject safety, when blood draws and other procedures coincide, blood draws will have precedence. A saline intravenous catheter may be used for blood collection to avoid multiple skin punctures, when appropriate. Otherwise, blood samples will be collected by direct venipuncture.

The total volume of blood including that collected for eligibility and safety purposes should not exceed 196 mL for the whole study (refer to [Table 3](#) for details). Deviations related to the volume of blood collected will be reported only when the total volume collected from a subject for the whole study is exceeded.

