Three changes in planned analyses were done compared to the protocol in this SAP: the PK primary endpoint of AUC_{0-72} was changed to AUC_{0-24} in order to better compare partial AUC across dose groups, the calculation of renal clearance (CL_R) was changed from Ae_{0-72}/AUC_{0-72} to Ae_{0-24}/AUC_{0-24} , and the PK endpoint of T_{max} was changed from a secondary endpoint to a primary endpoint. AUC_{0-72} remains in the analysis as a secondary endpoint. In addition, a clarification was added to indicate that the pharmacokinetic statistical comparisons (i.e.: Mild vs. Control, Moderate vs. Control, and Severe vs. Control) would be done separately.

Eloxx Pharmaceuticals

5. Primary and Secondary Endpoints

 AUC_{0-24} , AUC_{0-t} , AUC_{0-inf} , C_{max} and T_{max} calculated using plasma ELX-02 concentration data and Ae_{0-t} and R_{max} calculated using urine ELX-02 concentration data will be the primary PK endpoints. All other PK parameters calculated for ELX-02 will be regarded as secondary endpoints (refer to Section 10.3).

Safety and tolerability parameters are secondary endpoints (refer to Section 9).

Eloxx Pharmaceuticals

6. Analysis Populations

The analysis of safety and tolerability parameters will be based on the Safety population detailed in Section 6.1. The analysis of PK parameters will be based on the Pharmacokinetic population detailed in Section 6.2.

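### The SAP's linear trapezoidal rule, applied across the 6, 12 and 24 h samples, overstates AUC more in controls than in severe impairment; if it also governs AUC0-24, the Severe/Control ratio is about 1.4-6% too low

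*SAP*

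**What the plan says.** SAP 10.3.1 introduces all plasma parameters as derived by "standard non-compartmental methods". Only the AUC0-t entry names an integration rule: "calculated using the linear trapezoidal method". AUC0-inf is AUC0-t plus Ct/Kel, and CL/F and Vd/F are computed from AUC0-inf, so all three inherit that rule. AUC0-24 is defined only as "Area under the concentration-time curve from time zero to 24 hours post-dose", and AUC0-72 in the same way. Neither the SAP nor Protocol 12.1.1 mentions a logarithmic rule for the declining phase.

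SAP 10.3.1 gives the sampling times as "0.250, 0.500, 0.750, 1.00, 2.00, 4.00, 6.00, 12.0, 24.0, 36.0, 48.0, 72.0, and 168 hours post-dose", and Protocol 9.9.1 gives the same schedule. On half-life, Protocol 5.2.2.2 reports for 1 mg/kg in healthy subjects: "The half-life was 2.14" hours. Protocol 5.1.2 gives means "ranging between 2 to 4 hours for lower doses" (0.3 to 5.0 mg/kg).

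SAP Section 5 lists AUC0-24, AUC0-t and AUC0-inf among the parameters that "will be the primary PK endpoints". SAP 10.4 compares each impaired group with control by a geometric mean ratio and 90% CI. SAP 10.3.2 computes renal clearance as Ae0-24/AUC0-24.

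**The concern.** A straight line between two points on an exponential decline lies above the curve, so the linear rule overstates area there. The overstatement grows with the number of half-lives between samples. With a half-life of 2-4 h, the 6-12 h gap spans 1.5-3 half-lives and the 12-24 h gap spans 3-6. Renal impairment lengthens the half-life of a drug cleared mainly by the kidney, so the same gaps cover fewer half-lives and the error shrinks. An error that differs by group does not cancel in a group/control ratio.

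The ratios affected are primary endpoints, and the SAP intends the results to inform dosing recommendations. For AUC0-24 in severe impairment the error runs towards understating the renal effect. If AUC0-24 is integrated linearly, renal clearance is affected as well.

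**Working it through.** The documents give no figure for integration error, so there is nothing of theirs to reproduce. The check compares the trapezoidal area at the scheduled times with the exact area under a model curve.

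**Inputs from the documents.** CL/F 5.50 L/h, half-life 2.14 h and Tmax 1.0 h at 1 mg/kg (Protocol 5.2.2.2); half-life 2-4 h, urinary recovery 81.1-99.2% for SC doses and AUC CV 7.64-18.2% (Protocol 5.1.2); sampling times (SAP 10.3.1).

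**Assumptions.** One compartment with first-order absorption; V/F and ka unchanged by impairment. Severe clearance is not given, so it is projected as a fraction of control: 1 - fe x (1 - eGFR/eGFR of control), with fe 0.811-0.992, severe eGFR 15-29 and control eGFR 90-105. The extremes are 1 - 0.992 x (1 - 15/105) = 0.15 and 1 - 0.811 x (1 - 29/90) = 0.45. Moderate is taken as 0.48 and mild as 0.73-0.80.

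**Model.** C(t) is proportional to [ka/(ka - k)] x (exp(-kt) - exp(-ka t)), with k = ln 2/half-life and ka solved from ln(ka/k)/(ka - k) = 1 h. At 2.14 h, k = 0.324 per h, ka = 2.27 per h and V/F = 5.50/0.324 = 17 L. Mean residence time is 1/k + 1/ka = 3.5 h (protocol: 3-4 h). With a dose back-calculated as 5.50 x 13,131 = 72.2 mg (so partly circular), AUC0-12 is 12,813 against the reported 13,131 ng*h/mL, and Cmax is 3,076 against 3,576 ng/mL.

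**Error per interval.** For an exponential over a gap T the linear rule overstates area by x coth(x) - 1, with x = kT/2. At 2.14 h:
- 6-12 h: x = 0.97, error +30%. This gap holds 14.3% of AUC0-24, so it adds 4.25 points.
- 12-24 h: x = 1.94, error +102%. This gap holds 2.3% of AUC0-24, so it adds 2.40 points.
- 0-6 h adds the remaining 0.5 point. Total: +7.2%.

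At 25% of control clearance the half-life is 2.14/0.25 = 8.6 h, and the total error is only +2.5%.

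**AUC0-24 with the linear rule** (error in %; columns give severe clearance as a fraction of control):

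| Control half-life (h) | Control AUC | Severe AUC, 0.15 / 0.25 / 0.45 | Severe/Control ratio, 0.15 / 0.25 / 0.45 |
|---|---|---|---|
| 2.0 | +7.11 | +1.16 / +2.79 / +5.61 | -5.55 / -4.03 / -1.39 |
| 2.14 | +7.17 | +1.02 / +2.53 / +5.29 | -5.73 / -4.33 / -1.75 |
| 3.0 | +6.97 | +0.51 / +1.45 / +3.64 | -6.04 / -5.16 / -3.12 |
| 4.0 | +6.08 | +0.26 / +0.85 / +2.42 | -5.49 / -4.93 / -3.45 |

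Example at 2.14 h and 0.25: true ratio 3.41; linear rule 3.41 x 1.0253/1.0717 = 3.26.

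**Other contrasts.** Moderate/Control (0.48): -1.1% to -3.2%. Mild/Control (0.73-0.80): about 0 to -1.4%. The mild error is small because the bias is nearly flat for half-lives of 2-3 h.

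**Other models.** One matched to Cmax/AUC0-12 gives control +6.9% and severe ratio -1.5% to -4.1% (clearance 0.20-0.36). Four two-compartment models give control +6.5% to +6.9% and severe ratio -1.8% to -5.0% (clearance 0.15-0.36).

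**AUC0-inf.** At control half-life 2.14 h, severe clearance 0.15-0.25 and an assumed LLOQ of 0.5-50 ng/mL, the ratio error is -0.8% to -3.3%. At mild-like clearance of 0.73 it can reach +2.1%.

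**If the 24 h control sample is BLQ.** Modelled control concentration at 24 h is about 2 ng/mL at 2.14 h (1-38 ng/mL over half-lives of 2-4 h). SAP 10.1 sets a trailing BLQ value to missing. Control AUC0-t would then end at 12 h with a bias of +4.9%. Read literally, 10.3.1 would bar AUC0-24 for that subject.

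**Renal clearance.** With linear AUC0-24 at 2.14 h, it is low by 1 - 1/1.0717 = 6.7% in controls and 1 - 1/1.0253 = 2.5% at 0.25 clearance.

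**With linear-up/log-down.** Control AUC0-24 error is -0.5% to -1.1%, and the Severe/Control ratio error stays below +1%.

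**The case against.** The linear rule is an established non-compartmental method, is pre-specified for AUC0-t and applies identically to every group. The error is also small beside other features of the comparison. With 6 against 6-8 subjects and CV 7.64-18.2%, the 90% CI is about x/÷ 1.08 to 1.21. Stopping at 24 h by itself lowers a true ratio of 1/0.25 = 4.0 to 3.41, about 15%. AUC0-t and AUC0-inf are also primary, the SAP provides for regression on renal function if a clinically relevant effect appears, and it leaves room for additional analyses.

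Most of this stands as a limit on importance. It does not remove the point: identical application is what produces unequal errors when half-lives differ, a confidence interval does not cover a systematic error, and an optional extra analysis is not a commitment.

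Four stronger readings are tempting and are not supported:
- A reader might infer that the SAP prescribes the linear rule for AUC0-24. It does not say so; the words belong to AUC0-t.
- A reader might take the 4.3-5.7% error at 15-25% clearance and a 2.14 h half-life as the answer. Severe clearance is not in the documents, and the plausible range is wider. The printed spread of the half-life (± 2.14, equal to the mean) is also no guide.
- A reader might infer that CL/F and the AUC0-inf ratio carry the same downward error. That error is generally smaller, and its size and sign depend on the LLOQ and the clearance.
- A reader might infer that every contrast is materially distorted. Mild/Control barely moves.

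**Conclusion.** The point holds as a modest, avoidable bias. The linear rule is stated for AUC0-t, and hence for AUC0-inf, CL/F and Vd/F; for AUC0-24 and AUC0-72 it is the natural reading only. If applied to AUC0-24, it overstates control values by about 6-7% and severe values by about 0.3-5.6%, which makes the Severe/Control ratio about 1.4-6% too low. The direction for that ratio was the same in every model tried. The size rests on the assumed severe clearance of 15-45% of control, on V/F and ka unaffected by impairment, and on a quantifiable 24 h sample. Against an expected severe ratio of about 2-5 it would not change the qualitative finding that exposure rises. The reason to act is that the error is systematic, affects primary endpoints and is easily removed.

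**What to change.** In SAP 10.3.1, state linear-up/log-down as the single integration rule for AUC0-24, AUC0-72 and AUC0-t, and hence for AUC0-inf, CL/F, Vd/F and renal clearance. Say that it applies to both the interim analysis (SAP Section 7) and the final analysis. This also closes the gap that two of the AUCs have no named rule.

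The cost is one SAP sentence and one setting in the PK software. It needs no new samples or data and changes nothing for subjects.

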10.3.2 Urine Pharmacokinetic Parameters

For Group 1 to 4, Urine samples for PK analysis will be collected for each subject at the following time or time intervals: pre-dose (first void in the morning of Day 1), 0-3, 3-6, 6-9, 9-12, 12-18, 18-24, 24-36, 36-48, and 48-72 hours post-dose.

Urine concentrations from ELX-02 will be used to calculate the following parameters by standard non-compartmental methods:

Ae_{interval}: Amount of drug excreted in urine for each time interval, calculated as the

urine concentration multiplied by the urine volume.

Ae_{0-t}: Cumulative urinary excretion from time zero to time t, calculated as the sum

of the amounts excreted over each collection interval.

R_{max}: Maximum rate of urinary excretion, calculated by dividing the amount of drug

excreted in each collection interval by the time over which it was collected.

T_{Rmax}: Time of maximal urinary excretion, calculated as the midpoint of the collection

interval during which Rmax occurred.

Fe_{0-t}: Fraction (% dose) excreted unchanged, calculated as A_e/D_{sc}.

CL_R: Renal clearance, calculated as Ae₀₋₂₄ / AUC₀₋₂₄.

Additional pharmacokinetic analysis may be performed. Upon the Sponsor's request, pharmacokinetic repeats might be performed according to inVentiv's SOP. If re-assays are requested for pharmacokinetic reasons, final results will be presented using re-assay values, while results with original values will be presented in an appendix of the report as supportive data

Eloxx Pharmaceuticals

Some PK parameters may not be calculated for all or some subjects, at the discretion of the inVentiv pharmacokineticist, if the concentration data is not deemed to be amenable to evaluation. Explanations for PK parameters that could not be estimated will be provided in the PK report. Additional exploratory pharmacokinetic parameters such as urine half-life may also be assessed.

10.4 Statistical Analyses

Renal function assessment will be reported with the method using MDRD4 equation with serum creatinine concentration. GFR estimated with serum creatinine concentrations will be used to classify subjects and this classification will serve for primary analyses.

Individual and mean ($\pm SD$) plasma concentration versus time curves will be presented for both linear and semi-log scales. Descriptive statistics (arithmetic and geometric means, standard deviation [SD], coefficient of variation [CV%], minimum [Min], maximum [Max], and median) of the plasma concentrations versus time will be presented as well for the PK parameters according to renal function groups included in the study (Mild, Moderate, Severe renal impairment, and Control). A graphical description of the relationship between renal function measures and PK will be presented.

For plasma PK parameters, using GLM procedures in SAS, ANOVA will be performed on untransformed T_{max} , K_{el} and $T_{\frac{1}{2}el}$ and on In-transformed AUC_{0-24} , AUC_{0-72} , AUC_{0-t} , AUC_{0-inf} , and C_{max} . Factors incorporated in the model will include Group as a fixed effect. Each statistical comparison (i.e.: Mild vs. Control, Moderate vs. Control, and Severe vs. Control) will be done separately.

Sample code for the procedure in SAS® codes for ANOVA (Mild vs. Control) is specified below:

```
proc glm data=basepk;
where GROUP in ('1','4');
class GROUP;
model VAR = GROUP / ss3;
means GROUP;
lsmeans GROUP / cl alpha=0.1 pdiff;
estimate 'Mild vs. Control' GROUP 1 -1;
run;
```

The ratios of geometric means (Mild/Control, Moderate/Control, Severe/Control) and their associated 90% CI will be calculated according to ANOVA results for AUC_{0-24} , AUC_{0-72} , AUC_{0-t} , AUC_{0-inf} , and C_{max} . Inter-subject Coefficient of variation will be estimated. Two-sided p-values will also be derived as exploratory analyses to provide statistical inferences at the alpha 5% level of significance.

Derived calculations obtained from the ANOVA analyses will be performed as per the following:

• Inter Subject $CV = 100 * SQRT (e^{[MSE]} - 1);$

Eloxx Pharmaceuticals

- Ratio = 100 * e^{DIFFERENCE}, where DIFFERENCE is the point estimate of renal function groups difference (e.g. Mild Control, Mild Control, and Severe Control) on the Intransformed scale; and
- 90% Confidence Limits = 100 * e (DIFFERENCE ± t (dfResidual) * SE (dfResidual) * DIFFERENCE .

 T_{max} will be analyzed nonparametrically (using the Hodges-Lehmann method) with point estimates and 90% CIs for the median differences of Tmax between groups (Mild-Control, Moderate-Control, Severe-Control).

```
proc npar1way hl alpha=.10 data= basepk; class GROUP; var Tmax; exact hl; ods select WilcoxonScores HodgesLehmann; run;
```

For urine PK parameters, Ae_{0-t} and R_{max} will be analysed in the same manner as plasma PK parameters (AUC_{0-24} , AUC_{0-t} , AUC_{0-inf} , and C_{max}).

In the event that renal impairment has a clinically relevant effect on ELX-02 PK, the relationship between renal function and appropriate PK parameters for ELX-02 (e.g., CL/F, AUC_{0-24} , AUC_{0-72} , AUC_{0-1} , AUC_{0-inf} , and C_{max}) will be determined by a linear or non-linear regression.

Study results including the graphical description and the relationships between renal function and relevant pharmacokinetic parameters will be used to elaborate specific dosing recommendations if deemed clinically relevant.

Additional and exploratory statistical analysis may be performed.

11. Percentages and Decimal Places

If not otherwise specified, the following rules will be applied, with the exception of PK tables and listings described below:

- Percentages will be presented to one decimal point.
- Percentages equal to 0 or 100 will be presented as such without a decimal point.
- Minimum and maximum will be presented with the same precision as the original values and, mean, standard deviation, and median will be presented with one more decimal place than the original values.

All digits will be used for pharmacokinetic and statistical PK calculations. For PK tables and listings, the final reportable results or data will be presented by rounding off to two decimal digits, except for the following situations (this applies to individual data and descriptive statistics):

- K_{el} and correlation (Corr.) data: rounded off to four decimal digits.
- Pharmacokinetic parameters related to time such as T_{max}, K_{el Lower}, and K_{el Upper} must be reported with the same precision as the actual sampling time: rounded off to 3 decimal digits.
- Concentration versus time data, as well as C_{max}: reported as they appear in corresponding dataset.
- Ratios and 90% confidence intervals, and inter-CV (%) will be presented to two decimal places.

Eloxx Pharmaceuticals

12. Data Handling

The ELX-02 plasma and urine concentrations, safety and tolerability data will be received as SAS^{\circledast} datasets from the inVentiv data management facility. Screening failures and ineligible volunteer's data (subject disposition) will be received from the clinical site as source data.

Eloxx Pharmaceuticals

13. Handling of Missing Data

For PK, only observed data will be used in the data analysis except for concentration values BLQ and samples with no reportable value occurring prior to dosing as described in Section 10.1. No attempt will be made to extrapolate or interpolate estimates for missing data.

For safety,

- If an AE is recorded with an onset date corresponding to a dosing day, but the time is missing, then the AE will be assigned to the treatment as a TEAE.
- If an AE is recorded with an onset date that does not correspond to the dosing day, but the time is missing, then the AE will be assigned to the treatment as a TEAE if AE onset date is after dosing date.
- If an AE is recorded with an onset date where day and time are both missing, then the AE allocation to the treatment will be done on a case by case basis considering available information (e.g. AE end date, AE comments, subject disposition).

Eloxx Pharmaceuticals

14. Software to be Used

PK analysis will be performed using Phoenix WinNonlin® version 8 or higher, which is validated for bioequivalence/bioavailability studies by inVentiv. The safety data tables and listings, as well as PK tables and listings will be created using $SAS^{\textcircled{R}}$, release 9.2 or a higher version. PK figures will be created using R (version 3.5). The PK report text will be created using Microsoft® Office Word 2010, or a higher version.

Eloxx Pharmaceuticals

15. Reference List

None.

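### The primary urine endpoint Ae0-t is compared as an absolute amount under mg/kg dosing, so body weight enters its ratio and interval, while Fe0-t and CL_R have no planned ratio or 90% CI

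*SAP*

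**What the plan says.** SAP Section 3.3 sets a single dose of 1 mg/kg, calculated from the Day -1 weight. SAP Section 10.3.2 defines Ae0-t as a sum of excreted amounts and Rmax as an amount divided by collection time; neither is divided by dose. The same section defines Fe0-t ("Fraction (% dose) excreted unchanged, calculated as" Ae over the SC dose) and CL_R ("Renal clearance, calculated as" Ae0-24 over AUC0-24).

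SAP Section 5 makes Ae0-t and Rmax the two urine parameters among the primary endpoints ("calculated using urine ELX-02 concentration data will be the primary PK endpoints"). All other PK parameters, including Fe0-t and CL_R, are secondary.

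In SAP Section 10.4:

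- Model: "Factors incorporated in the model will include Group as a fixed effect". There is no weight or dose term.
- Ratios: "The ratios of geometric means (Mild/Control, Moderate/Control, Severe/Control) and their associated 90% CI will be calculated according to ANOVA results for" the plasma AUCs and Cmax. Ae0-t and Rmax then follow ("will be analysed in the same manner as plasma PK parameters"). Protocol Section 12.3.1 has the same urine list.
- Fe0-t and CL_R get descriptive statistics, including geometric means, which are planned "as well for the PK parameters according to renal function groups included in the study". They are in no ANOVA, ratio or interval list.
- If impairment has a clinically relevant effect, "the relationship between renal function and appropriate PK parameters for ELX-02" will be modelled by regression. The examples include CL/F but not CL_R.

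Controls are mean-matched on age, gender and BMI (SAP Section 3.1). Height and weight are not matching variables.

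**The concern.** The primary objective is the effect of renal impairment on the drug's PK. An amount excreted after mg/kg dosing mixes two things: the fraction of dose that reaches the urine, and how heavy the subject is. Only the first bears on the objective.

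Two consequences follow. A chance difference in mean weight shifts the Ae0-t ratio even if renal handling is identical. And weight spread within groups adds variance to the Ae0-t interval even if mean weights are equal; the plan invites such spread by seeking both genders and a range of BMIs in each group. Meanwhile the two calculated parameters that would avoid or bypass the problem have no interval estimate.

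**Working it through.** The documents give no precision calculation and no weight distribution, so there is no stated figure to reproduce. Weight CVs and the PK model below are assumptions.

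**1. Identity for Ae0-t.** Ae = Fe x dose, and dose = 1 mg/kg x weight. Hence GMR(Ae) = GMR(Fe) x GMR(weight), where GMR is the ratio of geometric means. At equal height, a 15% BMI difference (the matching tolerance) is a 15% weight difference, which moves the Ae0-t ratio by a factor of 1.15 or 1/1.15.

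**2. Interval width.** Inputs: 6 vs 6, df = 10, t(0.95, 10) = 1.812, the pairwise form in SAP Section 10.4.

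CI factor = exp(t x s x sqrt(1/6 + 1/6)), with s² = ln(1 + CVother²) + ln(1 + CVweight²), taking the two sources as independent. Fe0-t carries only the first term. Protocol Section 5.1.2 gives plasma AUC CVs of 7.64-18.2%; there is none for Fe, so 10% and 20% are used.

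| Other CV | Fe0-t | Ae0-t, weight CV 15% | 20% | 25% |
|---|---|---|---|---|
| 10% | x/÷1.11 | x/÷1.21 | x/÷1.26 | x/÷1.32 |
| 20% | x/÷1.23 | x/÷1.30 | x/÷1.34 | x/÷1.39 |

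**3. Rmax.** Rmax follows weight proportionally only if clearance does. Assume one compartment, V proportional to weight and CL proportional to weight^p. Baseline V = 5.50 x 2.14 / ln 2 = 16.98 L (CL/F and half-life from Protocol Section 5.2.2.2). For a mild group with GFR at 75% of normal and Fe 0.811, CL = 5.5 x (0.811 x 0.75 + 0.189) = 4.385 L/h and k = 0.2582 per h. Without an absorption phase, Rmax falls in 0-3 h and is proportional to weight x (1 - exp(-3k)). For a group 15% heavier:

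- p = 0: 1.15 x 0.4902 / 0.5392 = 1.045
- p = 0.5: 1.15 x 0.5144 / 0.5392 = 1.097
- p = 1: 1.15

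With Fe at 0.992 instead, or an absorption rate of 2 or 3 per h, the mild-group shift stays at about 4%, 9-10% and 15%. Dividing Rmax by dose would then leave an opposite error of about 9-10%, 5% and 0%.

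**4. What each parameter can show.** Same model, GFR at 75% / 45% / 20% of normal (assumed), CL_R proportional to GFR, constant non-renal clearance, and Fe 0.811-0.992 (SC urinary recovery, Protocol Section 5.1.2). Ratios to control without weight imbalance:

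| | Mild | Moderate | Severe |
|---|---|---|---|
| CL_R | 0.75 | 0.45 | 0.20 |
| Ae0-72 (Fe identical) | 0.94-1.00 | 0.81-0.99 | 0.57-0.96 |
| CL/F = Fe x GFR fraction + (1 - Fe) | 0.75-0.80 | 0.45-0.55 | 0.21-0.35 |

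A 15% weight difference would turn the mild Ae ratio into 1.08-1.15 (heavier) or 0.82-0.87 (lighter), which is larger than the effect being measured.

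**5. How likely is an imbalance?** With 6 vs 6, weight CV 15 / 20 / 25% and no help from matching, SE = sqrt(ln(1 + CV²)) x sqrt(2/6). The mean weights then differ by more than 15% with probability 2 x (1 - Φ(ln 1.15 / SE)) = 0.10 / 0.22 / 0.33. Gender and BMI matching would lower these, so they are upper-end illustrations.

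**The case against.** The strongest case against is that little is lost.

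- **Exposure is already covered.** AUC0-inf has a planned 90% CI. With 81.1-99.2% of SC doses recovered in urine, CL/F tracks CL_R closely in the mild group and fairly closely in the moderate group (step 4). This stands. The two can separate more in the severe group, but there the effect is large on either measure.
- **The information is partly there.** Fe0-t and CL_R have group geometric means, so point ratios can be read off. Weight is tabulated by group (SAP Section 8.3), a plot of renal function against PK is planned, the regression list is only exemplary, and additional analyses are allowed. This stands too, but none of it is a pre-specified interval, and with six per group a point ratio alone says little.
- **Fe0-t is no more sensitive than Ae0-t.** Correct. It removes the weight term but not the insensitivity to lost renal clearance, which is why CL_R is needed beside it.
- **CL_R in L/h is not free of body size.** Also correct. If it scales with weight to the power 0.5 to 1 (assumed), a 15% weight difference moves it by 1.15^0.5 = 1.07 to 1.15.

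A reader might go further and infer that Rmax carries the full weight factor. The documents do not show how clearance scales with weight, and step 3 gives the full factor only when it scales proportionally. A reader might also take 0.10-0.33 as the expected risk of imbalance; matching on gender, age and BMI is a Group 4 inclusion criterion (Protocol Section 8.3.1), so it is not.

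**Conclusion.** The point holds for Ae0-t and, in weaker form, for Rmax. The weight factor in the Ae0-t ratio is an identity and needs no model. Its size in this trial depends on a weight imbalance that the documents do not allow one to predict and that matching should restrain. The loss of precision does not need an imbalance: x/÷1.11 becomes x/÷1.21-1.32 at other CV 10%, and x/÷1.23 becomes x/÷1.30-1.39 at 20%, under assumed weight CVs of 15-25%.

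It would be wrong to conclude that weight could overturn the trial's exposure findings. The AUC0-inf comparisons are not at issue here, and the large moderate and severe effects on clearance would remain visible. What is missing is an interval for the renal pathway itself and a dose-free version of the primary urine comparison. This is a near-free improvement to the plan, not a flaw that threatens its main conclusion.

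**What to change.** In SAP Section 10.4:

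1. Add ln(Fe0-t) and ln(CL_R) to the ANOVA, with Mild/, Moderate/ and Severe/Control ratios and 90% CIs, beside the existing Ae0-t and Rmax rows.
2. Name CL_R beside CL/F in the regression on renal function.
3. State that CL_R in L/h can vary with body size. A BSA-indexed row is possible, because BSA is already calculated for corrected creatinine clearance (SAP Section 9.3).

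Rmax divided by dose is best left out, or shown only as a sensitivity row with the caveat that it may over-correct. The primary endpoint list in SAP Section 5 need not change.

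Cost: two table rows and two sentences. All inputs are already collected or calculated.
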